### Categorical DAS28 Response

- DAS28 (CRP) and DAS28 (ESR) will be categorized using EULAR response criteria. Response at a given time point is defined based on the combination of current DAS28 score and DAS28 decrease from baseline. The definition of no response, moderate response and good response is captured in the following table:
- DAS28 decrease from baseline value will be calculated using the following formula:

$$\text{DAS28 decrease from baseline} = \text{DAS28 Baseline} - \text{Post-Dose Visit DAS28 Value}$$

Current DAS28	DAS28 decrease from baseline		
	>1.2	>0.6 to $\leq 1.2$	$\leq 0.6$
$\leq 3.2$	Good response	Moderate response	No response
$>3.2$ to $\leq 5.1$	Moderate response	Moderate response	No response
$>5.1$	Moderate response	No response	No response

- If the post-baseline DAS28 (CRP) or DAS28 (ESR) is missing, then the corresponding EULAR category will be missing.

### DAS28 Remission

- DAS28 (CRP) remission is achieved by a DAS28 (CRP) value lower than 2.6.
- DAS28 (ESR) remission is achieved by a DAS28 (ESR) value lower than 2.6.
- Missing DAS28 values will be considered as not achieving remission.

### Health Assessment Questionnaire-Disability Index (HAQ-DI)[Fries, 1980; Matsuda, 2003]

#### Procedure

[figure not shown]
- The functional status of the subject will be assessed by means of the Disability Index of the Health Assessment Questionnaire. This 20-question instrument assesses the degree of difficulty a person has in accomplishing tasks in eight functional areas:
  - Dressing & grooming
  - Arising
  - Eating
  - Walking
  - Hygiene

- Reach
- Grip
- Activities
- Each functional area contains at least two questions. For each question, there is a four level response set that is scored from 0 (without any difficulty) to 3 (unable to do). If aids or devices or physical assistance are used for a specific functional area and the maximum response of this functional area is 0 or 1, the according value is increased to a score of 2.

Aid or device	Functional area
Devices used for dressing	Dressing and grooming
Special or built up chair	Arising
Built up or special utensils	Eating
Cane	Walking
Crutches	Walking
Walker	Walking
Wheelchair	Walking
Bathtub seat	Hygiene
Bathtub bar	Hygiene
Raised toilet seat	Hygiene
Long-handled appliances in bathroom	Hygiene
Long-handled appliances for reach	Reach
Jar opener	Grip

- Regarding these corrections, the highest response within each functional area determines the score of that specific functional area. If no questions within a given functional area were answered, no score will be provided for that category (even if answers on aids or equipment are available).
- HAQ-DI is only calculated if there are at least 6 functional area scores available.
- The average of these non-missing functional area scores defines the continuous HAQ-DI score ranging from 0 to 3. If there are less than 6 functional area scores available, no imputation will be done and the HAQ-DI will be set to missing for the according assessment.

## Flowchart

## Examples

## Value in each question

No.	Functional area	Value
1	Dressing and grooming	1
2	Dressing and grooming	0
3	Arising	2
4	Arising	1
5	Eating	3
6	Eating	0
7	Eating	2
8	Walking	1
9	Walking	0
10	Hygiene	2
11	Hygiene	2
12	Hygiene	1
13	Reach	0
14	Reach	0
15	Grip	3
16	Grip	2
17	Grip	0
18	Activities	2
19	Activities	1
20	Activities	0

## Use of aid or device / Need for help

Functional area	Use or Need
Dressing and grooming	×
Arising	○
Eating	×
Walking	○
Hygiene	×
Reach	○
Grip	×
Activities	×

Maximum value in each functional area

Functional area	Score	Use of aid	Updated score
Dressing and grooming	1	×	1
Arising	2	○	2
Eating	3	×	3
Walking	1	○	2
Hygiene	2	×	2
Reach	0	○	2
Grip	3	×	3
Activities	2	×	2
Sum updated scores			17
Divide by number of functional area scored			2.125

This score was not updated because it was more than 2

This score was increased to 2 because it was 0 or 1.

FACIT-Fatigue					
Procedure					

 
The FACIT-Fatigue questionnaire is a patient-reported measure developed to assess fatigue consisting 13 statements regarding feeling fatigue using a numeric rating scale ranging from 0 (Not at all) to 4 (very much).
 
For only two of the items (i.e. An5 and An7) a higher value represents a lower fatigue, 11 of the item scores (i.e. HI7, HI12, An1, An2, An3, An4, An8, An12, An14, An15, An16) have to be reversed by subtracting the captured value from 4 (0 is turned to a 4, 1 into 3, 3 into 1, 4 into 0).
 
After performing the reversals, the sum of the non-missing individual items will be multiplied by 13 and divided by the number of the non-missing individual items.
 
The final score ranges from 0 to 52 with higher values representing a lower fatigue.
 
If more than 6 individual items are missing at an assessment the FACIT-Fatigue score will be set to missing at that assessment.
 
					
Examples					
Item Code	Reverse Item		Item Response		Item Score
HI7	4	—	2	=	2
HI12	4	—	4	=	0
An1	4	—	3	=	1
An2	4	—	1	=	3
An3	4	—	3	=	1
An4	4	—	0	=	4
An5	0	+	2	=	2
An7	0	+	1	=	1
An8	4	—	2	=	2
An12	4	—	3	=	1
An14	4	—	1	=	3
An15	4	—	2	=	2
An16	4	—	3	=	1
Sum individual item scores				23	
Multiply by 13 =				299	
Divide by number of items answered =				23	
Fatigue Subscale Score =				23	
SDAI[Smolen, 2003]					

 
The Simplified Disease Activity Index (SDAI) is a composite score consisting of the sum of SJC28, TJC28, PtGA/10, PhGA/10, and CRP (mg/dl).
 
This score will be calculated based on the formula:
 
					
$SDAI = SJC28 + TJC28 + PtGA / 10 + PhGA / 10 + CRP$					

- If one of the components is missing at an individual assessment point, the SDAI value for that assessment will be set to missing.

#### CDAI[Aletaha, 2005]

- The Clinical Disease Activity Index (CDAI) is a composite score consisting of the sum of SJC28, TJC28, PtGA/10, PhGA/10.
- This score will be calculated based on the formula:

$$\text{CDAI} = \text{SJC28} + \text{TJC28} + \text{PtGA} / 10 + \text{PhGA} / 10$$

- If one of the components is missing at an individual assessment point, the CDAI value for that assessment will be set to missing.

#### Swollen and Tender/Painful Joint Count

- Four different scores will be calculated to evaluate swelling and tenderness of joints. SJC28 and TJC28 will take 28 joints into account, SJC66 and TJC68 will use 66 and 68 joints, respectively.
- The assessment for swelling is the total number of joints with a present swelling and ranges from 0 to 28 for SJC28 and 0 to 66 for SJC66.
- The assessment for tenderness is the total number of joints with a present tenderness and ranges from 0 to 28 for TJC28 and 0 to 68 for TJC68.
- The following 28 joints will be taken into account for TJC28 and SJC28.
  - Shoulder (2 joints)
  - Knee (2)
  - Elbow (2)
  - Wrist (2)
  - Fingers (PIP, MCP: 20)
- Additionally the following joints will be taken into account for TJC68 and SJC66.
  - Temporomandibular (2)
  - Sternoclavicular (2)
  - Acromioclavicular (2)
  - Fingers (DIP: 8)
  - Ankle (2)
  - Tarsus (2)
  - Toes (PIP, MTP: 20)
  - Hip (2, only for TJC)
- If there are missing observations for tender or swollen joints then the remaining observations will be assessed and weighted by dividing the number presented by number of non-missing and by multiplying by 28/66/68 for the joint count. No imputations for individual joints will be done. If a joint is not evaluable at Baseline, then that joint is set missing throughout the study.
- If data for more than 50% of the joints are missing at the time of a given assessment, then the total count will be set to missing for that visit.

**Patient's Assessment of Arthritis Pain**

- Subjects will assess the severity of their current arthritis pain using a continuous visual analogue scale (VAS) by placing a mark on the scale between "0" (no pain) and "10" (most severe pain), which corresponds to the magnitude of their current pain.
- Subjects will also assess the severity of their past week's arthritis pain using a continuous visual analogue scale (VAS) by placing a mark on the scale between "0" (no pain) and "100" (severe pain), which corresponds to the magnitude of their pain for the past week.
- The current endpoints are collected on eCRF after converted to a 100 unit.
- No imputations for missing data will be done.

**Patient's Global Assessment of Disease Activity**

- Subjects will complete a global assessment of disease activity using the patient global assessment (PtGA) item, a continuous VAS with anchors "0" (very well) to "10" (very poor).
- The current endpoints are collected on eCRF after converted to a 100 unit.
- No imputations for missing data will be done.

**Physician's Global Assessment of Arthritis**

- Physicians will complete a global assessment of disease activity using the physician global assessment item (PhGA), a continuous VAS with anchors "0" (none) to "10" (extremely active).
- The current endpoints are collected on eCRF after converted to a 100 unit.
- No imputations for missing data will be done.

### 11.5.5. Immunogenicity

**Immunogenicity**

- Samples taken after dosing with GSK3196165 that have a value at or above the cut-point will be considered treatment emergent Anti-Drug-Antibody positive.

## 11.6. Appendix 6: Premature Withdrawals & Handling of Missing Data

### 11.6.1. Premature Withdrawals

Element	Reporting Detail
General	
 
Subject study completion (i.e. as specified in the protocol) was defined as subjects who have completed all phases of the study including the following-up visit.
 
Withdrawn subjects were not replaced in the study.
 
All available data from subjects who were withdrawn from the study will be listed and all available planned data will be included in summary tables and figures, unless otherwise specified.
 

### 11.6.2. Handling of Missing Data

Element	Reporting Detail
General	
 
Missing data occurs when any requested data is not provided, leading to blank fields on the collection instrument : 
 
These data will be indicated by the use of a “blank” in subject listing displays. Unless all data for a specific visit are missing in which case the data is excluded from the table.
 
Answers such as “Not applicable” and “Not evaluable” are not considered to be missing data and should be displayed as such.
 
 
 

Binary variable	
 
Subjects with missing efficacy data or early withdrawal will be imputed as a failure (e.g. no DAS28(CRP) remission or no moderate/good EULAR response).
 

Continuous variable	
 
No imputation will be done.
 

### 11.6.2.1. Handling of Partial Dates

Element	Reporting Detail
General	Partial dates will be displayed as captured in subject listing displays.
Medications	
 
• Missing start day, but month and year present: 
 
◦ If first study medication administration had been taken place in the same month and year as the occurrence of the medication, then the start day of the medication is assigned to the day of first study medication administration.
 
◦ Otherwise the start day is set to the first day of the month (eg, XX-Sep-2010 is considered as 01-Sep-2010).
 
 
 
• Missing start day and month, but year present: 
 
◦ If first study medication administration had been taken in the same year as the occurrence of the medication, then the start date of the medication is assigned to the date of first study medication administration.
 
◦ Otherwise the start day and month is set to 01 January (eg, XX-XXX-2010 is considered as 01-Jan-2010).
 
 
 
• Missing stop day, but month and year present: 
 
◦ The day is set to the last day of the month (eg, XX-Sep-2010 is considered as 30-Sep-2010).
 
 
 
• Missing stop day and month, but year present: 
 
◦ The stop day and month is set to 31 December (eg, XX-XXX-2010 is considered as 31-Dec-2010).
 
 
 
• The recorded partial date will be displayed in listings.
 

RA diagnosis and symptom onset	
 
• Missing day, but month and year present: 
 
◦ Date is set to the first day of the month.
 
 
 
• Missing day and month, but year present: 
 
◦ Date is set to 01 January.
 
 
 

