6.10.1.1. Oral Corticosteroids

Stable use of oral corticosteroids \leq 10 mg/day prednisone or equivalent agent is permitted if the dose is stable for at least 4 weeks prior to Day 1 (baseline). This dose should remain constant throughout the first 12 weeks of the study. Dose changes before Week 12 are not permitted, unless required for safety or tolerability.

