### 11.3. Appendix 3: Treatment States and Phases

#### 11.3.1.1. Treatment States for Concomitant Medications for Rheumatoid Arthritis (CONMEDS RA) Data

Treatment State	Definition
Prior only	CONMEDs RA Stop Date < the Date of first dose of study medication
Prior and Concomitant	CONMEDs RA Start Date < the Date of first dose of study medication CONMEDs RA Stop Date $\geq$ the Date of first dose of study medication
Concomitant only	CONMEDs RA Start Date $\geq$ the Date of first dose of study medication

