
 
To assess corticosteroid use and determine average daily corticosteroid dose, all corticosteroid dosages will be converted to a prednisolone equivalent in milligrams by multiplying the dose of the steroid (using the coded term from GSKDrug) by the conversion factor to get prednisolone equivalent units.
 
The following table will provide the conversion factors.
 
For each scheduled visit, the average daily prednisolone dose will be calculated by summing all prednisolone doses since the previous visit up to and including the current visit and then dividing by the number of days in this period (Date of current visit – Date of previous scheduled visit).
 
If frequency that a subject takes the steroid is less than once daily such as QOD, the dosage will be converted to daily dose and then the average daily dose will be calculated. For example, if a subject takes 10 mg of the steroid QOD, the daily dose is 5 mg/day.
 
																

  
 Conversion	Steroid	
   
 8.333	BETAMETHASONE	
 
 0.2	CORTISONE	
 
 6.667	DEXAMETHASONE	
 
 0.25	HYDROCORTISONE	
 
 1.25	METHYLPREDNISOLONE	
 
 1	PREDNISOLONE	
 
 1.25	TRIAMCINOLONE	
  
	Conversion	Steroid	8.333	BETAMETHASONE	0.2	CORTISONE	6.667	DEXAMETHASONE	0.25	HYDROCORTISONE	1.25	METHYLPREDNISOLONE	1	PREDNISOLONE	1.25	TRIAMCINOLONE
Conversion	Steroid															
8.333	BETAMETHASONE															
0.2	CORTISONE															
6.667	DEXAMETHASONE															
0.25	HYDROCORTISONE															
1.25	METHYLPREDNISOLONE															
1	PREDNISOLONE															
1.25	TRIAMCINOLONE															
Rheumatoid factor (RF)																

 
A subject who has a value of RF <math>> 15</math> IU/mL is positive.
 
Otherwise negative.
 
																
Anti-cyclic Citrullinated Protein Antibody (ACPA)																

 
A subject who has a value of ACPA <math>\geq 4.5</math> U/mL is positive.
 
Otherwise negative.
 
																

Extent of Exposure																	
GSK3196165																	

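### A background RA drug whose start is recorded only as the year of first dose is imputed to start on Day 1, which eligibility rules out and which can show as a false steroid increase

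*SAP*

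**What the plan says.** SAP 11.6.2.1 (Handling of Partial Dates) has two branches for a partial medication start.

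- **Year only.** The condition reads "If first study medication administration had been taken in the same year as the occurrence of the medication". When it is met, the plan directs as follows: "then the start date of the medication is assigned to the date of first study medication administration". In every other case: "Otherwise the start day and month is set to 01 January (eg, XX-XXX-2010 is considered as 01-Jan-2010".
- **Month and year.** If they match the month and year of first dose, "then the start day of the medication is assigned to the day of first study medication administration". In every other case: "Otherwise the start day is set to the first day of the month (eg, XX-Sep-2010 is considered as 01-Sep-2010".

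Neither branch asks whether the drug was already being taken at Screening, and neither compares the imputed start with the stop date. The same section imputes RA diagnosis and symptom onset to the first of the month or 01 January without reference to first dose.

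Three other rules decide what an imputed start does.

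- SAP 11.3.1.1 classes an RA medication as Concomitant only when "CONMEDs RA Start Date $\geq$ the Date of first dose of study medication".
- SAP 11.5.2 forms the visit-average steroid dose by "summing all prednisolone doses since the previous visit up to and including the current visit", divided by the days between the current and previous scheduled visits.
- SAP 11.4.2.1 takes the latest pre-dose value as baseline.

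On eligibility, Protocol 6.10.1.1 says that low-dose oral steroid "is permitted if the dose is stable for at least 4 weeks prior to Day 1 (baseline"), and exclusion criterion 17 bars a new steroid or a dose change in that window. Inclusion criterion 8 requires MTX for at least 12 weeks before screening. Criterion 18 requires no new or changed NSAID for 2 weeks. Criterion 16 requires other conventional DMARDs to be stopped at least 2 weeks before Day 1.

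**The concern.** Imputing an unknown start to the first-dose date makes sense when a drug could have begun on either side of dosing. For background treatment that the protocol requires before Day 1, the answer is already known, and the rule chooses the one side that eligibility excludes.

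Two displays then mislead. A drug in use throughout screening drops out of the summary of RA medication before first dose (Table 1.16). A stable steroid user can also look like someone who started steroid on Day 1 (Tables 1.18 and 1.19). Steroid stability is something a reader checks before interpreting a DAS28 difference, and with 10 subjects per arm a single record is visible in an arm mean.

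**Working it through.** The plan gives no figure for this point. As a check on how the rule is read, applying it to the SAP's own examples returns 01-Sep-2010 and 01-Jan-2010 for starts, and 30-Sep-2010 and 31-Dec-2010 for stops.

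**Inputs**
- Screening of up to 28 days (Protocol 4.2); 7 to 28 days tried.
- Constant steroid dose of 2.5, 5 or 10 mg/day. The protocol ceiling is 10 mg/day; the two lower doses are illustrative.
- Arm size 10 (Protocol 9.2).
- Assumption 1: imputed dates feed the visit average. SAP 11.5.2 does not say so.
- Assumption 2: the baseline steroid value is the average over Screening to Day 1.

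**Affected record.** True start 1 February 2017, recorded as 2017 only, first dose 15 June 2017. The start is imputed to 15 June 2017 and the state is Concomitant only. With dose *D* and *n* screening days:

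- Baseline = *D* × 1/*n*, because only the Day 1 dose is counted.
- Week 1 average = *D* × 7/7 = *D*.
- False change = *D* × (1 − 1/*n*). The true change is 0.

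| Constant dose (mg/day) | *n* = 7 | *n* = 14 | *n* = 28 |
|---|---|---|---|
| 2.5 | +2.14 | +2.32 | +2.41 |
| 5 | +4.29 | +4.64 | +4.82 |
| 10 | +8.57 | +9.29 | +9.64 |

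For example, 5 − 5/28 = 5 − 0.18 = 4.82. The false change is 86% (6/7) to 96% (27/28) of the dose. If the Day 1 dose is not counted, baseline is 0 and the false change is the full dose. Because baseline is fixed, the error carries to each later visit while the dose stays constant.

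**Arm mean.** One such subject among 10, with non-users counted as zero: 4.29/10 = 0.43 up to 9.64/10 = 0.96 mg/day for doses of 5 to 10 mg/day. If the table averages over steroid users only, the divisor is smaller and the shift larger.

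**Records not affected** (first dose 15 June 2017, 10 mg/day, 28-day screening)
- 2014 only: imputed 01-Jan-2014, change 0.00.
- 2016 only: imputed 01-Jan-2016, change 0.00.
- February 2017, day missing: imputed 01-Feb-2017, change 0.00.

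**Same-month branch.** A steroid begun at least 28 days before Day 1 shares its calendar month only if Day 1 is the 29th to 31st, which is 29 of the 365 dates in 2017 (7.9%). MTX cannot share it. An NSAID needs only 14 days, so it can share the month when Day 1 is the 15th or later.

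**How far back a start can be moved.** The study period is December 2016 to January 2018 (Protocol 12.7.2). If Day 155 falls by 31 January 2018, the latest Day 1 is about 30 August 2017. A 2017 first dose can therefore displace a start by at most about 241 days (1 January to 30 August). A first dose at the end of December 2016 could displace one by up to 365 days.

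**Stop date.** Take a washed-out DMARD with start 2017 only, stop 30 April 2017 and first dose 15 June 2017. The imputed start, 15 June, falls after the stop. As the table in 11.3.1.1 is worded, the record meets both Prior only and Concomitant only.

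**After the fix.** The affected 10 mg/day record is imputed to 01-Jan-2017, with baseline 10.00, Week 1 10.00, change 0.00 and state Prior and Concomitant.

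**The case against.** The best defence is that the rule is narrow and its consequences small. Sites must verify steroid and MTX history to enrol a subject, so a start in the current year with the month unknown should be uncommon. No document counts such records. The eCRF is not available here and may carry a taken-before-study field. The flowchart after SAP 11.3.1.1 is not shown and may set an order that resolves the double classification. Treating an unknown start as concomitant also guards against missing an on-study start. All of this limits the point's importance. The last argument does not rescue the rule, though: it fits a drug whose timing relative to first dose is unknown, not one known to be in use at Screening.

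Several stronger readings are tempting, and the documents do not support them.

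- A reader might infer that long-standing medication in general is moved to Day 1. The fallback branches keep earlier-year and known-earlier-month starts before Day 1.
- A reader might take Tables 1.16 to 1.19 as the only view of background treatment. Table 1.15 (medications), Table 1.21 (MTX exposure) and Listing 16 are also planned, and listings show the partial date as recorded, so an imputed start can be traced by hand. SAP 6.1.5 also promises a by-visit steroid listing, although Appendix 10 contains none.
- A reader might suppose that a real on-study steroid start could be hidden. A year-only on-study start would still appear as a start, only moved to Day 1.
- A reader might think the DAS28 comparison is biased. The MMRM in SAP 8.2.2.1 contains dose, visit, baseline and their interactions with visit; no medication date enters it.

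**Conclusion.** The point holds for a defined set of records: medication already in use at Screening, with a start recorded only as the year of first dose, and in limited cases only as the month of first dose. For background RA drugs that eligibility places before Day 1, the imputed start is known to be wrong. The move to Concomitant only and the loss from Table 1.16 follow directly from the stated definitions.

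The steroid figures (about +4.3 to +4.8 mg/day at 5 mg/day, +8.6 to +9.6 at 10 mg/day, and +0.4 to +1.0 on a 10-subject arm mean) rest on the two assumptions in the working. The start-after-stop result follows from the text; whether it leads to double classification depends on a flowchart that is not shown.

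This is a minor correction. The number of affected records is unknown, and the effect is confined to descriptive medication tables. PK, adverse event and DAS28 analyses are untouched.

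**What to change.** In SAP 11.6.2.1, impute to the first-dose date only for medications first recorded after Day 1 dosing. For a medication recorded at Screening or before dosing on Day 1, or with a stop date before first dose, use the first of the recorded month or 01 January of the recorded year, and never a date later than the stop date. State in 11.5.2 whether imputed dates feed the visit-average steroid dose and which interval gives its baseline. Produce Tables 1.16 to 1.19 on that rule.

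The cost is a sentence or two of SAP text and one programming condition. Concomitant medication is already collected at Screening and Day 1 in the Time and Events Table, so no new data are needed.

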### **6.1.4. RA disease history**

RA disease history will be summarized in form of disease duration categorical (< 2 years/  $\geq$  2 years) and as summary statistics (in month), RA functional class and time since start of RA symptoms. Disease duration and time since start of RA symptoms are defined in the Appendix 5.

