### 11.5.2. Study Population

Demographics
Age

 
GSK standard IDSL algorithms will be used for calculating age where birth date will be imputed as follows: 
 
Any subject with a missing date and month will have this imputed as ‘30th June’.
 
Birth date will be presented in listings as ‘YYYY’.
 
Age will be calculated based on date of Screening visit as an Age reference date for Screen failed subjects and based on date of the initial dose date for ITT population.
 
 
 

Age Group

 
The following category will be used for Summary of Demography. 
 
Age ≤ 18 (years)
 
19 < Age < 64
 
65 ≤ Age
 
 
 

Age Category

 
The following category will be used for Summary of Age Ranges. 
 
Age < 18 (years)
 
18 ≤ Age ≤ 64
 
65 ≤ Age ≤ 84
 
85 ≤ Age
 
 
 

Body Mass Index (BMI)

 
Calculated as Weight (kg) / [Height (m)]
 

Demographics																
RA disease history																
RA Disease Duration																

 
RA disease duration will be calculated based on the formula:  <math display="block">\text{Disease Duration in Months} = [\text{Treatment Start Date} - (\text{RA Diagnosis Date})] / 30.25</math> 
rounded to four decimals
 <math display="block">\text{Disease Duration in Years} = [\text{Treatment Start Date} - (\text{RA Diagnosis Date})] / 365.25</math> 
rounded to four decimals
 
 
																
Time since start of RA symptoms																

 
Time since start of RA symptoms will be calculated based on the formula:  <math display="block">\text{Time since start of RA symptoms in Months} = [\text{Treatment Start Date} - (\text{Date of first symptom})] / 30.25</math> 
rounded to four decimals
 
 
																
Prior and Concomitant Medications																
Oral Corticosteroid																

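### RA duration in months is divided by 30.25 days, which conflicts with the SAP's own 365.25-day year and overstates every month value by 0.62%; separately, partial RA dates are always set to the earliest possible day

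*SAP*

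**What the plan says.** SAP 11.5.2 introduces the derivation with "RA disease duration will be calculated based on the formula" and then gives two versions. Each starts from treatment start date minus diagnosis date in days; the month version divides by 30.25 and the year version by 365.25. Time since first symptom is given in months only, again with 30.25.

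SAP 6.1.4 sets the display: "RA disease history will be summarized in form of disease duration categorical", with classes below 2 years and 2 years or more, alongside summary statistics in months. It does not say in words which formula feeds the class.

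SAP 11.6.2.1 covers partial diagnosis and symptom dates. With the day missing: "Date is set to the first day of the month". With day and month missing: "Date is set to 01 January".

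For birth date, SAP 11.5.2 takes a central value: "Any subject with a missing date and month will have this imputed as" 30 June.

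**The concern.** There are two separate faults, and both push reported duration upward.

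The first is a plain inconsistency. One baseline table would carry a class in years and statistics in months that rest on calendars of different length. Anyone converting the month figures back to years would get a slightly different answer from the class formula.

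The second is the direction of the date imputation. The earliest possible day is always chosen, so the error never cancels across subjects. For a year-only date the error can be large relative to a 2-year cut. With 10 subjects planned per arm (Protocol 9.2), one subject in the wrong class moves that arm's percentage by 10 points in the table that describes the groups.

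**Working it through.** **Inputs**
- Divisors 30.25 and 365.25: SAP 11.5.2.
- Class in years, statistics in months: SAP 6.1.4.
- Imputation rules: SAP 11.6.2.1.
- Study period December 2016 to January 2018 (Protocol 12.7.2) and last visit on Day 155 (Protocol 7.1). Assumption drawn from these: first doses fall between about December 2016 and August 2017.
- At least 12 weeks (84 days) since symptom onset: Protocol 5.1, criterion 4.

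**1. Can 30.25 be reproduced?** 365/12 = 30.4167; 365.25/12 = 30.4375; 366/12 = 30.5. None gives 30.25, and 12 × 30.25 = 363 days.

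**2. Size of the month error.** 30.4375/30.25 − 1 = 0.62%.

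| True duration (years) | SAP months (years × 365.25/30.25) | Consistent months | Excess |
|---|---|---|---|
| 2 | 24.15 | 24 | 0.15 |
| 5 | 60.37 | 60 | 0.37 |
| 10 | 120.74 | 120 | 0.74 |
| 20 | 241.49 | 240 | 1.49 |

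**3. Does the divisor move the class?** In years, the class is days/365.25 ≥ 2, a cut at 2 × 365.25 = 730.5 days. The 30.25 does not enter. Only if the class were programmed as months ≥ 24 would the cut fall to 24 × 30.25 = 726 days, and durations of 726 to 730 days would then be classed differently.

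**4. Year-only dates under the 1 January rule.** The error runs from 0 to +364 days (+365 in a leap year). Counting all dates in a 365-day year equally, the mean is 182 days, about 6 months. For a 2017 start from 2 January on, a year-only 2015 diagnosis is always classed as 2 years or more. The true 2015 dates that are really under 2 years are:

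| First dose | Duration from 1 Jan 2015 (years) | True 2015 dates under 2 years |
|---|---|---|
| 2 Jan 2017 | 2.00 | 363/365 (99%) |
| 1 Mar 2017 | 2.16 | 305/365 (84%) |
| 1 May 2017 | 2.33 | 244/365 (67%) |
| 1 Aug 2017 | 2.58 | 152/365 (42%) |

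For a first dose on 15 December 2016, a year-only 2014 date is wrong for 16 of 365 true dates, and a 2015 date (imputed 1.95 years) stays correctly below 2. Year-only dates from other years are not misclassified in these scenarios.

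**5. Dates lacking only the day.** Same direction, at most 30 days. Example: first dose 15 March 2017, diagnosis recorded as March 2015. The rule gives 745/365.25 = 2.04 years; if the true date was 31 March, it is 715/365.25 = 1.96.

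**6. Mid-year alternative.** In a 365-day year 30 June is day 181, so the error runs from −180 to +184 days, with mean +2. For a 2015 year-only date:

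| First dose | Wrong under 1 January | Wrong under mid-year |
|---|---|---|
| 1 Mar 2017 | 305 upward | 60 downward |
| 1 May 2017 | 244 upward | 121 downward |
| 1 Aug 2017 | 152 upward | 152 upward |

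The mean bias nearly vanishes. Misclassification falls or stays the same, but does not disappear.

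**7. Why mid-year needs a bound.** With a first dose on 1 July 2017 and symptom onset recorded only as 2017, 30 June gives 1 day since symptoms, against the required 84. The 1 January rule gives 181 days. For an earlier 2017 start, 30 June can fall after the first dose.

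**The case against.** The strongest reply is that nothing inferential depends on this. Disease history feeds Table 1.14 and Listing 14. It is not a term in the MMRM, the dose-response models or the PK power model, and no hypothesis is tested. Partial dates are listed as captured, so an affected subject can be identified. All of this stands, and it keeps the point minor.

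The birth-date comparison is also weaker than it looks. Protocol 7.2 collects only year of birth, so a central value is routine there. The closer parallel is the medication start-date rule in the same SAP table, which also uses the first of the month or 1 January unless the first dose falls in that month or year. The RA rule therefore largely follows a convention already in the SAP. That explains the choice but does not change its direction.

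Mid-year imputation also has a cost. Without a bound it can contradict eligibility, as step 7 shows.

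A reader might infer that the divisor and the imputation together push subjects over the 2-year line. The documents do not support that: the class is in years, and the years formula uses 365.25. A reader might also infer a fixed misclassified share, such as half of those with one to two years of disease. That share depends on when subjects start, and the documents do not say how many dates are year-only; there may be none.

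**Conclusion.** The month divisor is wrong as written. It overstates every month value for disease duration and for time since symptoms by 0.62%, whatever the data look like. It leaves the 2-year class alone, on the natural reading that a class in years uses the formula in years.

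The imputation rule is a separate, one-way bias of 0 to about 12 months for year-only dates and at most 30 days when only the day is missing. It can misclassify a subject only when the partial date spans the 2-year cut-off; for year-only dates and 2017 starts, that means 2015. The shares in step 4 rest on assumed first-dose dates and on counting all days of the year equally. The number of affected subjects is unknown.

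The consequence is confined to the descriptive baseline displays. Nothing here bears on the PK, safety or efficacy analyses.

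**What to change.** - SAP 11.5.2: replace 30.25 with 30.4375 (365.25/12) in both month formulas.
- SAP 6.1.4 or 11.5.2: state that the 2-year class is derived from days/365.25.
- SAP 11.6.2.1: for RA diagnosis and symptom onset, set a year-only date to 30 June and a date lacking only the day to the 15th. Bound the result so that neither date falls after the first dose and the symptom date does not contradict the 12-week criterion.
- Table 1.14: footnote the number of imputed dates per arm, so that the reader can see whether the rule mattered.

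The cost is a few SAP lines and a re-run of one table and its listing, with no new data and no model change. Under the new rule an imputed duration can err in either direction, and some misclassification at 2 years remains.
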